8.4 Assessment of Causal Relationship

The investigator will assess the relationship of an adverse event to study product as related or not related (ie, if there is a reasonable possibility that the study product caused the event), and document the relationship in the subject's source documents.

8.5 Assessment of Severity (Intensity)

Severity describes the intensity of a specific adverse event (eg, mild, moderate, severe, life-threatening, or death). The particular event may be of relatively minor medical significance (such as severe headache). Severity is not the same as "serious," which is based on subject/event outcome or action criteria.

Investigators will grade the severity of adverse events. The severity of an adverse event is to be recorded on the case report form and in the subject's source documents.

Three different severity grading systems will be used depending on type of adverse event: allergic reactions, anaphylaxis, or all other adverse events. Brief descriptions of the 3 severity grading systems are provided.

Severity of allergic reactions will be graded using the Consortium of Food Allergy Research (CoFAR) grading system (adapted from [Burks, 2012](#)), with scores ranging from 1 (transient or mild discomfort) to 5 (death) ([Table 7](#)).

Table 7: CoFAR Severity Grading System for Allergic Reactions

Grade 1 Mild	Grade 2 Moderate	Grade 3 Severe	Grade 4 Life-Threatening	Grade 5 Death
Transient or mild discomforts (< 48 hours), no or minimal medical intervention/therapy required.	Symptoms that produce mild to moderate limitation in activity, some assistance may be needed; no or minimal intervention/therapy is required. Hospitalization is possible.	Marked limitation in activity, some assistance usually required; medical intervention/therapy required, hospitalization is possible. Parenteral medication(s) are usually indicated.	Extreme limitation in activity, significant assistance required; significant medical/ therapy. Intervention is required; hospitalization is probable.	Death
Symptoms may include pruritus, swelling or rash, abdominal discomfort, or other transient symptoms.	Symptoms may include persistent hives, wheezing without dyspnea, abdominal discomfort/ increased vomiting, or other symptoms.	Symptoms may include bronchospasm with dyspnea, severe abdominal pain, throat tightness with hoarseness, transient hypotension, or other symptoms.	Symptoms may include persistent hypotension and/or hypoxia with resultant decreased level of consciousness associated with collapse and/or incontinence, or other life-threatening symptoms.	

Source: Adapted from [Burks, 2012](#).

CoFAR, Consortium of Food Allergy Research.

Severity of anaphylaxis will be graded according to the modified EAACI guidelines ([Table 8](#); adapted from [Muraro, 2007](#)). The clinical assessment of anaphylaxis is described in [Section 8.6.1.1](#).

Table 8: Modified EAACI Severity Grading System for Anaphylaxis

Severity Grade	Description	Symptoms
1 – Mild	Involves skin and subcutaneous tissues, gastrointestinal, and/or mild respiratory	Flushing; urticaria; periorbital edema or facial angioedema; mild dyspnea, wheeze, or upper respiratory symptoms; mild abdominal pain and/or emesis
2 – Moderate	Involves mild symptoms and features suggesting moderate respiratory, cardiovascular, or gastrointestinal symptoms	Marked dysphagia, hoarseness, and/or stridor; shortness of breath, wheezing, and retractions; crampy abdominal pain, recurrent vomiting, and/or diarrhea; and/or mild dizziness
3 – Severe	Involves hypoxia, hypotension, or neurologic compromise	Cyanosis or $\text{SpO}_2 \leq 92\%$ at any stage, hypotension [1], confusion, collapse, loss of consciousness, or incontinence

Source: Adapted from [Muraro, 2007](#).[1] Systolic blood pressure: $< 70 \text{ mm Hg}$ in subjects aged 1 month to 1 year, $< (70 \text{ mm Hg} + [2 \times \text{age}])$ in subjects aged > 1 to 10 years.

EAACI, European Academy of Allergy and Clinical Immunology.

Severity of all other adverse events will be graded according to the National Cancer Institute (NCI) Common Terminology Criteria for Adverse Events (CTCAE). CTCAE terms are grouped by system organ class, graded 1 to 5, and have unique clinical descriptions of severity for each adverse event based on the general guideline presented in [Table 9](#).

Table 9: NCI CTCAE Severity Grading System for Adverse Events

Grade 1 Mild	Grade 2 Moderate	Grade 3 Severe	Grade 4 Life-Threatening	Grade 5 Death
Asymptomatic or mild symptoms; clinical or diagnostic observations only; intervention not indicated	Minimal, local, or noninvasive intervention indicated; limiting age-appropriate instrumental activities of daily living	Severe or medically significant but not immediately life-threatening; hospitalization or prolongation of hospitalization indicated; disabling; limiting self-care activities of daily living	Life-threatening consequences; urgent intervention indicated	Death

Source: NCI CTCAE.

NCI CTCAE, National Cancer Institute Common Terminology Criteria for Adverse Events.

8.6 Special Safety Considerations

This section provides guidelines for the assessment of allergic reactions (including assessment of anaphylaxis and tolerability of a dose), treatment of allergic reactions, study

product dose adjustments due to allergic reactions or other reasons, missed doses of study product, adverse events of interest, and overdose. The assessment and treatment of allergic reactions resulting from accidental and nonaccidental food allergen exposure should follow the same guidelines as allergic reactions resulting from study product.

8.6.1 Assessment of Allergic Reactions

Allergy symptoms may occur during treatment with study product as observed in other desensitization protocols. Subjects must be observed for at least 90 minutes after completion of a dose or dose escalation at the study site, with vital sign measurements and assessment for symptoms of allergic reaction performed 15 to 30 minutes postdose and every approximately 30 minutes thereafter. The postdose observation period during maintenance treatment may be shortened to approximately 30 minutes if no allergy symptoms occurred during the previous 3 maintenance visits.

The length of observation will be extended beyond 90 minutes if symptoms of allergic reaction develop as follows:

- Mild symptoms: observe for at least 90 minutes or at least 1 hour after symptoms resolve, whichever is longer.
- Moderate symptoms: observe for at least 2 hours after symptoms resolve.
- Severe symptoms: observe for at least 3 hours after symptoms resolve either at the study site or an emergency facility, as appropriate. Consider extended overnight observation if symptoms are protracted.
- Life-threatening symptoms: observe at an emergency facility for as long as needed consistent with good medical practice. Consider extended overnight observation if symptoms are protracted.

Depending on the subject's stage of development, certain allergy symptoms may be difficult to interpret. Subtle symptoms may include ear picking, tongue rubbing, putting a hand in the mouth, and neck scratching ([Bird, 2017](#)). Other symptoms of allergic reaction may include persistent rubbing of the nose or eyes, irritability, clinging to the parent/caregiver, inconsolable crying, somnolence, and drawing legs up to the abdomen.

The assessing physician will determine whether the allergy symptoms meet the criteria for dose-limiting symptoms ([Section 8.6.1.2](#)).

The severity of symptoms of an allergic reaction will be assessed as described in [Section 8.5](#).

Signs and symptoms of allergic reactions will be recorded on the case report form and in the subject's source documents.

8.6.1.1 Assessment of Anaphylaxis

Anaphylaxis is defined by a number of signs and symptoms, alone or in combination, that occur within minutes up to a few hours after exposure to a provoking agent. Anaphylaxis

can be mild, moderate, or severe ([Section 8.5](#)). Adverse events of anaphylaxis are considered adverse events of interest and require rapid reporting as described in [Section 8.7.2](#).

Anaphylaxis is likely when any of the following 3 criteria for suspected anaphylaxis is fulfilled (adapted from [Sampson, 2006](#)):

1. Acute onset of an illness (minutes to hours) with involvement of the skin, mucosal tissue, or both (eg, generalized hives, pruritus or flushing, swollen lips/tongue/uvula) and at least 1 of the following:
 - Respiratory compromise (eg, dyspnea, wheeze/bronchospasm, stridor, hypoxemia)
 - Reduced blood pressure or associated symptoms of end-organ dysfunction (eg, hypotonia, syncope, incontinence)
2. Two or more of the following that occur rapidly after exposure to a likely allergen for the subject (minutes to hours):
 - Involvement of the skin/mucosal tissue (eg, generalized hives, itch/flush, swollen lips/tongue/uvula)
 - Respiratory compromise (eg, dyspnea, wheeze/bronchospasm, stridor, hypoxemia)
 - Reduced blood pressure or associated symptoms (eg, hypotonia, syncope, incontinence)
 - Persistent GI symptoms (eg, nausea, crampy abdominal pain, vomiting)
3. Reduced blood pressure after exposure to a known allergen for the subject (minutes to hours) as follows:
 - Infants and children: > 30% decrease from baseline in systolic blood pressure or low systolic blood pressure in children defined as follows:
 - Aged 1 month to 1 year: < 70 mm Hg
 - Aged > 1 to 10 years: < (70 mm Hg + [2 × age])

Potential signs of anaphylaxis in young children may be difficult to interpret because they include behaviors typical for their stage of development, including irritability, clinging to the parent/caregiver, inconsolable crying, and somnolence ([Bird, 2017](#)).

8.6.1.2 Assessment of the Tolerability of a Study Product Dose or Dose Level

The tolerability of a study product dose or dose level will be assessed based on the occurrence of acute allergy symptoms after dosing. When multiple symptoms are present, the severity of the most severe symptom will be used to determine whether symptoms are dose limiting and the dose or dose level is tolerated. Possible assessments of symptom severity, dose-limiting symptoms, and dose tolerability are shown in [Table 10](#).

Table 10: Allergy Symptom Severity and Study Product Dose Tolerability

Symptom Severity [1]	Dose-Limiting Symptom	Assessed Tolerability of Dose
None	No	Tolerated
Mild, oropharyngeal symptoms only	No	Tolerated
Mild, meeting tolerability criteria	No	Tolerated
Mild, not meeting tolerability criteria	Yes	Not tolerated
Moderate, with rare exceptions	Yes	Not tolerated
Severe	Yes	Not tolerated
Life-threatening	Yes	Not tolerated

[1] Depending on the subject's stage of development, allergy symptoms may be difficult to interpret. Age-appropriate allergy symptoms should be considered when assessing the tolerability of a dose.

No Symptoms: A study product dose associated with no allergy symptoms will be assessed as tolerated.

Mild symptoms: For a study product dose associated with mild allergy symptoms, investigator assessment is essential in determining if the symptoms are dose limiting. Based on experience with study product, mild symptoms are not dose limiting if they meet all of the tolerability criteria as follows:

- Are isolated to a single organ system
- Resolve with no medications or with ≤ 2 doses of oral H1 antihistamine
- Do not require administration of epinephrine
- Do not worsen in intensity or distribution over time
- Resolve or show definite signs of resolving in under 1 hour
- Do not include objective wheezing

The study product dose is to be considered not tolerated if mild symptoms do not meet the tolerability criteria as follows:

- Occur in 2 or more organ systems
- Require treatment with 3 doses of oral H1 antihistamine or 1 dose of epinephrine
- Progress in severity or distribution over time
- Continue longer than expected
- Include objective wheezing

If a study product dose associated with mild symptoms that do not meet the tolerability criteria is assessed as tolerated by the investigator, an explanation must be provided on the case report form.

Guidelines for recurrent mild symptoms:

- GI symptoms were the most common subacute, chronic, and recurrent potential symptoms of allergy in phase 2 and 3 clinical studies of AR101.
- Study product may worsen pre-existing atopic dermatitis, seasonal allergies, or asthma, or these symptoms may occur as nonacute allergic reactions to study product.
- Recurrent mild symptoms during several days of dosing at home suggest that the study product dose level is likely not tolerated, even if the symptoms meet the tolerability criteria. For mild dose-related symptoms occurring \geq 7 times within 2 weeks, the dose level is to be considered not tolerated.

Moderate symptoms: A study product dose associated with moderate allergy symptoms will be assessed as not tolerated, except on rare occasions such as a transient, self-limited symptom in a single organ system that requires no intervention, resolves completely, and is typically subjective.

If a study product dose associated with moderate symptoms is assessed as tolerated by the investigator, an explanation must be provided on the case report form.

Severe symptoms: A study product dose associated with severe allergy symptoms will be assessed as not tolerated.

Life-threatening symptoms: A study product dose associated with life-threatening allergy symptoms will be assessed as not tolerated.

8.6.2 Treatment of Allergic Reactions

Treatment of allergic reactions is guided by the type of symptoms and severity as determined by the investigator, and supplements dose adjustment. Rescue medications for acute allergic reactions include antihistamines, epinephrine, IV fluids, a beta-agonist (eg, albuterol by inhaler or nebulizer), oxygen, and glucocorticosteroids as indicated ([Section 7.3](#)).

Mild acute allergic reactions are mostly transient and self-limiting and require no therapeutic intervention, whereas other reactions may require treatment (generally antihistamines).

Treatment for chronic or recurrent allergic reactions should be used minimally and discontinued as soon as clinically appropriate. Treatment for chronic or recurrent allergic reactions should not be started in advance of symptoms; however, exceptions may be allowed on a case-by-case basis following approval from the medical monitor.

Moderate acute allergic reactions will generally require therapeutic intervention; some rare events may be so transient that no specific treatment is required. For moderate reactions requiring treatment, antihistamines and/or epinephrine is to be administered as indicated.

Severe acute allergic reactions will generally require treatment with epinephrine.

Life-threatening acute allergic reactions will require treatment at an emergency facility as appropriate and consistent with good medical practice.

If the severity of the reaction is uncertain, epinephrine administration is likely appropriate.

A medical monitor will be available to answer questions or to assist in decisions related to the study protocol.

8.6.3 Dose Adjustment of Study Product for Allergic Reactions

8.6.3.1 Dose Adjustment of Study Product During Initial Dose Escalation (Days 1 and 2)

Actions that may be taken with study product for allergic reactions occurring on day 1 of initial dose escalation include the following:

- Extend the time interval between study product doses (up to an additional 30 minutes) without any additional treatment.
- Initiate enhanced clinical monitoring (eg, more frequent vital sign monitoring and/or auscultation).
- Treat with antihistamine and resume study product dose escalation within 60 minutes after the previous dose, if assessed as safe.
- Treat with epinephrine, beta-agonist, oxygen, IV fluids, > 2 doses of antihistamines, and/or glucocorticosteroids as necessary. Stop the initial dose escalation and discontinue the subject early from the study if these rescue medications are used at any study product dose ([Section 5.3](#)).
- Stop the initial dose escalation and discontinue the subject early from the study.

The process algorithm for actions to be taken with study product dosing and treatment for acute allergy symptoms on initial dose-escalation day 1 is shown in [Figure 2](#) and described in [Table 11](#). The same process algorithm for actions to be taken with study product dosing and treatment for acute allergy symptoms is to be followed for allergic reactions occurring on day 2 of initial dose escalation.

Figure 2: Management of Study Product Dosing for Allergy Symptoms on Initial Dose-Escalation Day 1

[figure not shown]

Table 11: Description of Actions to Be Taken With Study Product Dosing for Allergy Symptoms on Initial Dose-Escalation Day 1

Symptoms [1]	Actions
Mild	
For oral/pharyngeal pruritus occurring in isolation, advance to the next dose of study product in 30 minutes.
 
For other mild symptoms, either:
 
 Advance to the next dose of study product in 30 to 60 minutes. Treat with antihistamine, then resume dose escalation within 60 minutes after the previous dose if signs and symptoms resolve to minimal or residual, and the investigator considers continued dosing to be safe. 
If only 1 or 2 doses of antihistamine are used to treat mild symptoms, the initial dose escalation may continue.
 
If a second medication (eg, epinephrine or a beta-agonist) or > 2 doses of antihistamines are needed, stop the initial dose escalation and discontinue the subject early from the study, even if the symptoms are assessed as mild.
 
Use of epinephrine, although unlikely to be used to treat mild dose-related symptoms, will stop the initial dose escalation and discontinue the subject early from the study.

Moderate	
For moderate symptoms not worsening in intensity or distribution over time, the investigator may take a stepwise approach to treatment. Treatment may be initiated immediately or after observation. If the first action is observation, observation should not exceed 30 minutes before starting treatment if symptoms have not resolved. Initiate treatment with antihistamines or administer epinephrine immediately as appropriate. Initiate other therapies sequentially or concurrently per investigator judgment.
 
Stop the initial dose escalation and discontinue the subject early from the study.

Severe	
For severe symptoms at any dose, administer the appropriate rescue medications.
 
Stop the initial dose escalation and discontinue the subject from study early.

Life-threatening	
For life-threatening symptoms at any dose, administer the appropriate rescue medications and treatment per standard of care. Stop the initial dose escalation and discontinue the subject from study early.

At any study product dose on initial dose-escalation day 1 or 2, treatment with epinephrine, beta-agonist, oxygen, IV fluids, > 2 doses of antihistamines, and/or glucocorticosteroids will stop the initial dose escalation and discontinue the subject early from the study (Section 5.3).

[1] Depending on the subject's stage of development, allergy symptoms may be difficult to interpret. Age-appropriate allergy symptoms should be considered when determining the appropriate actions to be taken with study product dosing.

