3 INVESTIGATIONAL PLAN

3.1 Overall Study Design and Plan: Description

This is a phase 3, international, randomized, double-blind, placebo-controlled study of the efficacy and safety of AR101 in peanut-allergic children aged 1 to < 4 years. The study will be conducted at approximately 25 study sites in North America and Europe.

Eligible subjects who develop age-appropriate dose-limiting allergy symptoms after consuming single doses of peanut protein > 3 mg to \leq 300 mg in a screening DBPCFC will be randomly assigned 2:1 to blinded treatment with AR101 or placebo. Randomization will be stratified by geographic region (North America, Europe).

Subjects will begin initial dose escalation under medical supervision at the study site on day 1 with a stepwise dose escalation of study product (up to 4 single doses of 0.5, 1, 1.5, and 3 mg) administered at 20- to 30-minute intervals as tolerated. Subjects who tolerate the 3 mg dose on day 1 will return on day 2 for a single 1 mg dose. Subjects who tolerate the 1 mg dose with no more than mild allergy symptoms that are not dose-limiting will begin the up-dosing period. Subjects who do not tolerate any dose on day 1 or day 2 will discontinue early from the study.

The up-dosing period will be approximately 6 months (maximum 40 weeks), with dose escalation approximately every 2 weeks. Daily doses of study product during up-dosing will be 1, 3, 6, 12, 20, 40, 80, 120, 160, 200, 240, and 300 mg/day. The first dose of study product at each new dose level will be administered under medical supervision at the study site; the remaining doses at each dose level will be administered daily at home as tolerated. Dose adjustments may be allowed. Subjects who tolerate the 300 mg/day dose for 2 weeks within 40 weeks will begin the maintenance period. Subjects unable to tolerate the 300 mg/day dose for 2 weeks within 40 weeks of up-dosing will discontinue early from the study.

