5.2.3 General Study Visit Procedures

Day 1 will be the first day of randomized study treatment (AR101 or placebo). Study procedures will be performed at each visit according to the schedule of activities ([Appendix 5](#)).

Before administration of the first and any subsequent dose of study product at the study site, the subject's health status must be at baseline state, including no presence of active wheezing, flare of atopic disease (eg, atopic dermatitis), or suspected intercurrent illness. The subject must have fully recovered from any previous illness for at least 3 days, depending on the severity of the illness per investigator assessment.

A study physician must always be readily available during dosing at the study site. Signs and symptoms of an allergic reaction will be evaluated, and monitoring will continue through the end of the observation period as follows:

- Symptoms of allergic reactions will be evaluated per [Section 8.6.1](#).
- The tolerability of study product will be evaluated per [Section 8.6.1.2](#).
- The treatment of allergic reactions and dose adjustment of study product will follow guidelines per [Section 8.6.2](#) and [Section 8.6.3](#).

On the day after each study site visit, site staff will contact the parent/caregiver by telephone to perform the following ([Appendix 5](#)):

- Inquire if any adverse events occurred (including allergy symptoms, GI symptoms, and exposure to food allergen).
- Provide guidance in managing adverse events.
- Remind the parent/caregiver to record the subject's symptoms in the study diary.
- Inquire about compliance with study product dosing.

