5.2.3.1 Initial Dose-Escalation Procedures

Initial dose-escalation procedures are listed in [Appendix 5](#). Subjects may have clear liquids or flavored gelatin during the dosing procedures.

Day 1

Subjects will be required to discontinue antihistamines and other medications that could interfere with the assessment of an allergic reaction for 5 half-lives of the medication before the first day of dose escalation.

Study product will be administered in 4 increasing doses in a stepwise manner in 20- to 30-minute intervals as tolerated. The 4 doses and cumulative dose of study product to be consumed on day 1 are shown in [Table 1](#).

Table 1: Study Product Single Doses and Cumulative Dose on Day 1

Dose Number	Study Product Dose (mg)	Cumulative Dose (mg)
1	0.5	0.5
2	1	1.5
3	1.5	3
4	3	6

The time points for study product dosing and assessments of vital signs and allergic reaction are provided in [Table 2](#). Subjects who develop dose-limiting, moderate, or severe allergy symptoms at any dose of study product, or use rescue medications (except ≤ 2 doses of antihistamines, [Section 8.6.3.1](#)) will stop dose escalation and discontinue early from the study ([Section 5.3](#)).

Table 2: Initial Dose-Escalation Day 1 Procedures

Study Product Dose (Timing) Time Point	Administer Study Product	Vital Signs [1]	Assess Allergy Symptoms
Predose		X	
0.5 mg	X		
15-30 min postdose		X	X
1 mg (20-30 min after previous dose) [2]	X		
15-30 min postdose		X	X
1.5 mg (20-30 min after previous dose) [2]	X		
15-30 min postdose		X	X
3 mg (20-30 min after previous dose) [2]	X		
15-30 min postdose		X	X
Approximately every 30 min until at least 90 min after last dose or end of observation per allergy symptoms [3]		X	X

[1] Vital signs include blood pressure, heart rate, temperature, respiratory rate, and oxygen saturation level.

[2] If the previous dose was tolerated ([Section 8.6.1.2](#)). If the subject has dose-limiting, moderate, or severe symptoms at any dose, or requires rescue medications (except ≤ 2 doses of antihistamines, [Section 8.6.3.1](#)), stop dose escalation and discontinue the subject early from the study. If 3 mg is tolerated, the subject will return for a single 1 mg dose on day 2.

[3] The length of observation is based on signs/symptoms of allergic reaction per [Section 8.6.1](#).
Min, minutes.

Day 2

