Adverse event or intercurrent illness	
Any intolerable adverse event that cannot be ameliorated using adequate medical intervention or that in the opinion of the investigator or sponsor may lead to undue risk if study treatment were continued, such as the following:
 
• Life-threatening symptoms (CoFAR grade 4), including anaphylaxis resulting in hypotension, neurologic compromise, or mechanical ventilation secondary to study treatment or food challenge.• Severe dose-related allergic hypersensitivity symptoms (CoFAR grade 3) that require intensive therapy (per investigator assessment, but may include interventions such as IV epinephrine, intubation, or admission to an intensive care unit) or are recurrent.• Poor control or persistent activation of secondary atopic disease (eg, atopic dermatitis, asthma).• Development of biopsy-documented eosinophilic esophagitis. 
Any adverse event that meets the early discontinuation criteria for study product tolerability or delays as follows:
 
• Tolerability of study product:
– Dose-limiting, moderate, or severe symptoms at any dose on initial dose-escalation day 1 or 2– Dose withheld for > 4 weeks for chronic or recurrent gastrointestinal adverse events at ≤ 20 mg/day– Unable to tolerate the 300 mg/day dose for 2 weeks within 40 weeks of up-dosing• Use of rescue medications:
– Treatment with epinephrine, beta-agonist, oxygen, IV fluids, > 2 doses of antihistamines, and/or glucocorticosteroids at any study product dose on initial dose-escalation day 1 or 2

Category Reason	Comment on Criteria

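### Table 11 allows another day 1 dose after mild symptoms that the rest of the protocol treats as a reason to stop

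*Combined protocol and SAP*

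**What the plan says.** Section 5.2.3 governs every dosing visit at the site. It has tolerability evaluated under Section 8.6.1.2 and adds: "The treatment of allergic reactions and dose adjustment of study product will follow guidelines per" Sections 8.6.2 and 8.6.3. Sites are therefore sent to both places.

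**The rule in the procedural sections.** In Section 5.2.3.1, Table 2 footnote [2] puts a condition on the 1, 1.5 and 3 mg doses: "If the previous dose was tolerated", with a reference to Section 8.6.1.2. The same footnote gives the stop rule: "If the subject has dose-limiting, moderate, or severe symptoms at any dose, or requires rescue medications" (up to two antihistamine doses excepted), escalation ends and the child leaves the study. The body text of 5.2.3.1 says the same. Table 4 in Section 5.3 lists as a discontinuation criterion "Dose-limiting, moderate, or severe symptoms at any dose on initial dose-escalation day 1 or 2". Section 3.1 states: "Subjects who do not tolerate any dose on day 1 or day 2 will discontinue early from the study".

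**What makes mild symptoms dose-limiting.** Section 8.6.1.2 sets a default: "The study product dose is to be considered not tolerated if mild symptoms do not meet the tolerability criteria as follows". The grounds are involvement of two or more organ systems, a need for three antihistamine doses or one of epinephrine, progression, longer duration than expected, and objective wheezing. Table 10 marks such symptoms as dose-limiting. The investigator may still assess the dose as tolerated, with an explanation on the case report form.

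**The rule in Table 11.** For mild symptoms other than isolated oral or pharyngeal itching, the day 1 action table gives two alternatives. One is "Advance to the next dose of study product in 30 to 60 minutes". The other is to give an antihistamine and resume "if signs and symptoms resolve to minimal or residual, and the investigator considers continued dosing to be safe". The row's only instructions to stop concern medication: a second drug, more than two antihistamine doses, or epinephrine.

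**The concern.** The same reaction can lead to opposite actions depending on which table the site has open. Under the procedural sections, mild symptoms that fail the 8.6.1.2 criteria end day 1 and end participation. Under Table 11 read literally, the child may receive the next dose.

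The first alternative in Table 11 is also less guarded than the second. A treated child must show resolution and a judgment that continuing is safe; an untreated child need show neither.

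What is at stake is consistency of a safety rule in children aged 1 to < 4 years, whose symptoms the protocol itself describes as hard to interpret. It is not a matter of power, error rate or the primary endpoint.

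**Working it through.** There is no stated statistical figure to reproduce. The check is a comparison of text, followed by simple arithmetic on Table 1.

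**Step 1. Each 8.6.1.2 ground against Table 11's mild row.** For every ground, footnote [2], Section 5.2.3.1 and Table 4 require stopping unless the investigator documents that the dose was tolerated.

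| Ground for a dose with mild symptoms being not tolerated | Does Table 11 stop escalation? |
|---|---|
| Two or more organ systems | No |
| Three antihistamine doses, or epinephrine | Yes, by the medication rule |
| Progression in severity or distribution | Not while symptoms stay mild; yes once moderate |
| Longer than expected | No |
| Objective wheezing | Not in the mild row; usually yes through the moderate row, because CoFAR (Table 7) gives wheezing without dyspnea as a moderate example |

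The mild row itself catches one ground, medication. Two more are caught wholly or partly when grading moves the child to the moderate row. What remains is untreated mild symptoms in two or more organ systems, spread within the mild grade, and prolonged mild symptoms.

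**Step 2. A worked case.** After the 1 mg dose a child has a few hives and a runny nose, no drug is given, and no override is documented. The severity guide for food challenges (Appendix 1, Table 3) lists both as mild, one under skin and one under respiratory. Two organ systems are involved, so 8.6.1.2 makes the dose not tolerated. Footnote [2] and Table 4 then discontinue the child. Table 11 allows the 1.5 mg dose.

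**Step 3. Comparison with Table 12.** For up-dosing and maintenance, Table 12 separates mild symptoms assessed as tolerated from those assessed as not tolerated, and its note refers to 8.6.1.2. Table 11 does neither. The general action list in 8.6.3.1 includes stopping, but only as an available action, with no criterion for mild symptoms.

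**Step 4. Size of the gap.** Table 1 gives doses of 0.5, 1, 1.5 and 3 mg. The cumulative doses reproduce: 0.5; 0.5 + 1 = 1.5; 1.5 + 1.5 = 3; 3 + 3 = 6 mg. The ratio is next dose / dose just given. The amount still possible is 6 mg minus the cumulative dose.

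| Symptoms after | Next dose | Ratio | Still possible on day 1 |
|---|---|---|---|
| 0.5 mg | 1 mg | 1 / 0.5 = 2 | 6 − 0.5 = 5.5 mg |
| 1 mg | 1.5 mg | 1.5 / 1 = 1.5 | 6 − 1.5 = 4.5 mg |
| 1.5 mg | 3 mg | 3 / 1.5 = 2 | 6 − 3 = 3 mg |
| 3 mg | none | – | 0 mg |

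The conflict can therefore arise at 3 of the 4 steps.

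**Step 5. Day 2.** Section 8.6.3.1 applies the same algorithm on day 2, but day 2 has a single 1 mg dose and its own stop rule in 5.2.3.1. No further dose is at issue that day, so day 2 is not part of this point.

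**The case against.** The strongest reply is that the rule is already in the protocol, several times. Footnote [2] can be read as deciding whether a next dose is allowed, with Table 11 setting only the interval and treatment once it is. Nothing in Table 11 claims to override the footnote, and Section 5.2.3 tells sites to apply 8.6.1.2 and 8.6.3 together. That reading is reasonable and is probably what was meant. It makes this an inconsistency and not a missing rule. It does not remove the conflict: Table 11 does address when mild symptoms stop escalation and names only medication triggers, so a reader may take that list as complete. No text was found that says which provision prevails.

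Second, Section 8.6.3.1 presents the day 1 algorithm in Figure 2 as well as Table 11, and the figure is not in the text available. Figure 3, its counterpart for later periods, carries a tolerability note. Figure 2 may hold the branch; this stays open. If it does, figure and table still need to agree.

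Third, the uncaught set is narrow, and 8.6.1.2 gives the investigator discretion. That stands, as step 1 shows. The override requires a written explanation, however, and Table 11 does not mention it.

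Fourth, the doses are small. Eligible children reacted at screening to single doses above 3 mg, and the screening challenge includes 1 and 3 mg steps (4 mg cumulative). Day 1 follows within 10 days. Every single dose at issue is thus no larger than one recently taken without dose-limiting symptoms, and the full day 1 total exceeds that cumulative amount by 6 − 4 = 2 mg. This limits the likely harm and the likely number of cases. It does not justify dosing a child who has just met the protocol's stop rule.

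**Conclusion.** The concern holds. Table 11's mild row, followed literally, permits a further day 1 dose in a child whom Sections 3.1 and 5.2.3.1, Table 2 footnote [2] and Table 4 would discontinue. The clearest case is untreated mild symptoms in two organ systems with no documented override.

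The exposure is bounded: 3 of 4 steps, a next dose of 1 to 3 mg, and at most 5.5 mg more that day, under supervision with at least 90 minutes of observation after the last dose. The protocol gives no number of children affected, and it may be small.

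The conclusion rests on the text of Table 11 alone and would weigh less if Figure 2 contains the tolerability branch. The correction should be made as a matter of safety consistency; no effect on the primary endpoint is shown.

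**What to change.** Split the mild row of Table 11 in the way Table 12 already does:

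- If the dose is assessed as tolerated under Section 8.6.1.2, keep the existing advance and antihistamine alternatives.
- If it is assessed as not tolerated, stop the initial dose escalation and discontinue the child under Section 5.3.

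Add a note under the table referring tolerability assessment to Section 8.6.1.2. Check Figure 2 and add the same branch if it is absent.

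The cost is one table row and one footnote in an amendment, plus the figure if needed. No procedure, visit, sample size or analysis changes.
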